6. STUDY POPULATION

6.1. Patient Disposition

Number of patients in each analysis set will be summarized. The number and percentage of patients who were randomized, who received at least one dose of study drug, who completed the study treatment, and who prematurely discontinued from the study treatment and/or from the study, will be presented by each dose level and overall, as well as by baseline riluzole and

edaravone use status. Reasons for premature discontinuation as recorded on the termination page of the eCRF will be summarized as well.

All enrolled patients will be listed with their date of screening, date of last visit, dates of first and last dose, demographic information including age, sex, race, last contact date, and reasons for discontinuation from the study treatment and/or from the study.

6.2. Screen Failures

Number and percentage of screen failures will be summarized by reasons of screening failure. A listing will also be provided.

6.3. Protocol Deviations

Protocol deviation is any divergence from the protocol that impacts a patient's safety, rights, or welfare or materially reduces the quality or completeness of the data. Number and percentage of patients meeting any protocol deviation criteria will be summarized by type of deviation (major, minor), dose level and overall. A listing of protocol deviations will be provided.

6.4. Demographic and Baseline Characteristics

Demographic and baseline characteristics which include age, sex, race, ethnicity, height, weight, BMI, tobacco and alcohol use, etc. will be summarized overall, by dose level and by riluzole and edaravone use status at baseline. Patient listings will be provided.

6.5. Listing of Patient Inclusion and Exclusion Criteria

A listing of randomized patients who violate the inclusion and exclusion criteria will be provided.

6.6. Medical History and Medical Conditions Present at Entry

Medical history will be summarized by dose level and overall for the safety population. The number and percentage of patients within each medical history item will be summarized by system organ class and preferred term. Patient listings with start date, stop date, system organ class, and preferred term will be provided.

Medical history of ALS will be summarized by dose level and overall for the safety population. The number and percentage of patients with or without family history, onset site of ALS, and the descriptive statistics of time since first symptom onset and time since first diagnosis will be provided. Patient listing containing symptom onset date, and diagnosis date will be provided.

6.7. Prior Medication History and Medications Present at Entry

Prior medication history and medication present at entry will be coded using WHO Drug Dictionary Enhanced with Herbal, June 2015 to classify medications by therapeutic class (ATC Class 3) and preferred name. If ATC Class 3 is not available, ATC Class 2 will be used in the summary. See [Section 5.5.10.4](#) for the definition of prior medications.

6.8. Baseline Physical Examination

Clinically significant physical examination findings will be summarized as medical history or AEs, as appropriate.

6.9. Baseline Vital Signs

Baseline vital signs such as heart rate, blood pressure, respiratory rate and BMI will be summarized and listed along with post baseline vital signs.

6.10. Baseline Laboratory Data

Baseline laboratory data of hematology, serum chemistry and urinalysis will be summarized and provided in the table along with post baseline laboratory data. The laboratory parameters to be included for analysis are given in appendices of the protocol.

6.11. Baseline Primary and Secondary Efficacy Evaluations

Baseline primary and secondary efficacy evaluation will be summarized and listed along with post baseline efficacy evaluation.

7. EFFICACY

Inferential statistical tests will be two-sided and will be performed at alpha levels of 0.05 to declare the significance of effects.

7.1. Testing Statistical Assumptions

Assumptions for statistical models will be evaluated graphically. If assumptions are substantially violated, additional analysis methods will be performed.

7.2. Statement of the Null and Alternate Hypotheses

The statistical null hypothesis is that there is no treatment difference between the two high dose groups combined and placebo group plus low dose group (ie, 600 mg/day and 900 mg/day dose groups combined vs. placebo and 300 mg/day dose groups combined) with the assumed dose-response relationship in percent predicted SVC change from baseline to Week 12. The statistical alternative hypothesis is that there is a positive treatment difference (reldesemtiv minus placebo) in change from baseline to Week 12 in the percent predicted SVC.

Suppose the means of the efficacy endpoint for the placebo, 300 mg/day, 600 mg/day and 900 mg/day dose groups are μ_{placebo} , $\mu_{\text{300 mg/day}}$, $\mu_{\text{600 mg/day}}$ and $\mu_{\text{900 mg/day}}$, respectively. With the assumed dose-response relationship for the means among the placebo, 300 mg/day, 600 mg/day and 900 mg/day dose groups, the null and alternative hypotheses can be expressed as follows:

- $H_0: -5 \times \mu_{\text{placebo}} - 1 \times \mu_{\text{300 mg/day}} + 3 \times \mu_{\text{600 mg/day}} + 3 \times \mu_{\text{900 mg/day}} = 0$
- $H_A: -5 \times \mu_{\text{placebo}} - 1 \times \mu_{\text{300 mg/day}} + 3 \times \mu_{\text{600 mg/day}} + 3 \times \mu_{\text{900 mg/day}} \neq 0$

7.3. Subgroup Analyses

To examine the consistency of the observed treatment effect and to gain insight into the effectiveness of reldesemtiv in subpopulations, subgroup analyses will be performed. Analyses of the primary endpoint (percent predicted SVC change from baseline to Week 12) and the secondary endpoints (slope of muscle strength mega score through Week 12, and ALSFRS-R score change from baseline to Week 12) will be conducted for the following subgroups if the sample size in each category of a subgroup is sufficient for statistical modeling convergence and sound interpretation of analysis results:

- Sex (male, female)
- Age group (< 65, ≥ 65 years old)
- Race (white, non-white)
- BMI at baseline (< 25 kg/m², ≥ 25 kg/m²)
- Riluzole and edaravone use status at baseline (use both, use riluzole only, use edaravone only, use neither)
- Percent predicted SVC at baseline (< 80%, ≥ 80%)
- ALSFRS-R total score at baseline (< 38, ≥ 38)
- ALSAQ-5 total score at baseline (< 150, ≥ 150)
- Geographic region (North America, Europe, Australia)
- Anatomic site of disease onset (limb, bulbar, cognitive, respiratory)
- Time since ALS symptom onset (< 2 years, ≥ 2 years)
- Time since ALS diagnosis (< 1 year, ≥ 1 year)
- Time since ALS diagnosis (< 6 months, ≥ 6 months)
- Pre-study rate of disease progression (1st tertile, 2nd tertile, and 3rd tertile)

7.4. Multiple Comparisons and Multiplicity

The null hypothesis for the primary and secondary efficacy endpoints will be tested in a prespecified order using a closed testing procedure. This procedure will maintain the family-wise error rate at two-sided significance level of 0.05 for all primary and secondary hypotheses tested in a confirmatory sense.

- Step 1. The null hypothesis H_{01} is that there is no treatment difference in the primary efficacy endpoint, percent predicted SVC change from baseline to Week 12, in the FAS. The hypothesis will be tested at the two-sided significance level of 0.05. If this hypothesis is rejected, testing will proceed to Step 2; otherwise testing will stop.
- Step 2. The null hypotheses H_{02} is that there is no treatment difference in the secondary efficacy endpoint, slope of muscle strength mega score through Week 12, in the FAS.

The hypotheses will be tested at the two-sided significance level of 0.05. If this hypothesis is rejected, testing will proceed to Step 3; otherwise testing will stop.

Step 3. The null hypotheses H_{03} is that there is no treatment difference in the secondary efficacy endpoint, ALSFRS-R total score change from baseline to Week 12, in the FAS. The hypotheses will be tested at the two-sided significance level of 0.05.

No further hypothesis testing will be carried out in this closed testing procedure.

7.5. Analysis of the Primary Efficacy Endpoints

7.5.1. Primary Efficacy Analysis

The primary efficacy endpoint (change from baseline to Visit Week 12 in percent predicted SVC) will be analyzed for the FAS based on the percent predicted SVCs collected in clinic and were confirmed evaluable by the central read of an independent pulmonologist. A MMRM with the contrast (-5, -1, 3, 3) will be used for the analysis to reflect the assumed relationship for the placebo, 300 mg/day, 600 mg/day and 900 mg/day dose groups. The response variable will be the change from baseline to each post baseline visit up to Week 12. The model will include the following covariates:

- Treatment (reldesemtiv 300 mg/day, 600 mg/day and 900 mg/day, and placebo)
- Baseline (baseline value of the response variable)
- Pooled site (Center)
- Visit (scheduled, a categorical variable)
- Riluzole and edaravone use status at baseline
- Treatment-by-visit interaction
- Baseline-by-visit interaction

An unstructured variance-covariance structure will be used to model the within-subject errors. If a model fails to converge, other covariance matrix structures (eg, compound symmetry) may be used instead of the unstructured covariance matrix. Least square means and the corresponding standard errors, 95% CIs and p-values will be presented.

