8.1.2. Sample Size and Randomization

Approximately 445 patients will be randomized to receive either one of the three CK-2127107 doses (300 mg/day, 600 mg/day and 900 mg/day TDD) or matching placebo tablets in a ratio of 1:1:1:1. Randomization will be stratified by riluzole use/non-use and edaravone use/non-use. The dropout rate at Visit Week 12 is estimated to be 10%, thus approximately 400 patients are expected to complete 12 weeks of double-blind treatment. The effect of CK-2127107 on the change from baseline to Week 12 in percent predicted SVC will be analyzed using a mixed model for repeated measures (MMRM) with the contrast (-5, -1, 3, 3) to reflect the assumed relationship for the placebo, 300 mg/day, 600 mg/day and 900 mg/day dose groups. The analysis is estimated to provide 90% power to detect 2.75, 5.5 and 5.5 percentage points advantage over placebo for the 300 mg/day, 600 mg/day and 900 mg/day CK-2127107 dose groups, respectively, in change from baseline of percent predicted SVC, at the end of the double-blind treatment (Visit Week 12). This calculation is based on a two-sided test with alpha set at 0.05 and a common standard deviation of 14 percentage points.

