3.3. Sample Size Consideration

3.3.1. Sample Size Justification

Approximately 445 patients will be randomized. The dropout rate at Visit Week 12 is estimated to be 10%, thus approximately 400 patients are expected to complete 12 weeks of double-blind treatment. The effect of reldesemtiv on the change from baseline to Week 12 in percent predicted SVC will be analyzed using a mixed model for repeated measures (MMRM) with the contrast (-5, -1, 3, 3) to reflect the assumed relationship for the placebo, 300 mg/day, 600 mg/day and 900 mg/day dose groups. The sample size is estimated to provide 90% power to detect 2.75, 5.5 and 5.5 percentage points advantage over placebo in the change from baseline to Visit Week 12 of

percent predicted SVC for the 300 mg/day, 600 mg/day and 900 mg/day reldesemtiv dose groups, respectively. This calculation is based on a two-sided test with alpha set at 0.05 and a common standard deviation (SD) of 14 percentage points.

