7.7. Analysis of the Exploratory Efficacy Endpoints

Analyses for the exploratory endpoints specified in [Section 2.2.4](#) will be performed for the FAS.

The endpoints of change from baseline will be analyzed using the same model as described for the primary efficacy endpoint, except for the response variable.

The endpoint of percent change from baseline or muscle strength mega score (calculated as percent change in muscle strength from baseline) will be analyzed using the same model as described for the primary efficacy endpoint, except that the terms “baseline” and “baseline-by-visit interaction” will be excluded from the model.

The endpoints of slope of the change from baseline will be analyzed using a MMRM. The response variable will be the change from baseline to each post baseline visit up to Week 12. The model will include the following covariates:

- Treatment (reldesemtiv 300 mg/day, 600 mg/day and 900 mg/day, and placebo)
- Baseline (baseline value of the response variable)
- Pooled site (Center)
- Time (time from the first dose, a continuous variable)
- Riluzole and edaravone use status at baseline
- Treatment-by-baseline
- Treatment-by-time interaction

The time will be set as a random effect and the intercept will be set to zero.

The endpoints of slope of percent change from baseline, including slope of percent change in parameters of handwriting and voice recording, will be analyzed using the same model as for the slope of muscle strength mega score over time described in [Section 7.6](#).

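### The MMRM fallback in SAP 7.5.1 has no fixed order, and its only example, compound symmetry, can understate the Week 12 standard error if it is used (minor)

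*SAP*

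**What the plan says.** Protocol 8.4.4.1 specifies an unstructured covariance for the primary MMRM and has no fallback. SAP 7.5.1 keeps the unstructured matrix and adds one: "If a model fails to converge, other covariance matrix structures (eg, compound symmetry) may be used instead of the unstructured covariance matrix". It ranks no alternatives, names no structure with visit-specific variances, and mentions no robust standard error. SAP 7.9.3.2 repeats the provision for the combined home and clinic SVC model.

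Other analyses inherit the primary model. SAP 7.6 uses it for ALSFRS-R. SAP 7.7 states: "The endpoints of change from baseline will be analyzed using the same model as described for the primary efficacy endpoint". That covers SVC measured at home. SAP 7.3 plans subgroup analyses of the primary and secondary endpoints, but only where each category is large enough for the model to converge and be interpreted.

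The prototype code in SAP 13 uses type = un with Kenward-Roger degrees of freedom on Weeks 2, 4, 8 and 12. For variability, the documents give a single figure, a "common standard deviation (SD) of 14 percentage points" (SAP 3.3.1).

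**The concern.** Compound symmetry forces the same variance at Weeks 2, 4, 8 and 12. Patients with a progressive disease decline at different rates, so their changes from baseline usually spread apart over time. The SAP models them that way: its slope analysis of change from baseline (7.7) has a random effect on time and a zero intercept, which implies variance that rises with time. Pooling the variance over visits then understates it at Week 12, the visit that is tested. The standard error, confidence interval and p-value all err in the anti-conservative direction. Kenward-Roger does not cure this, because it adjusts for small samples within the assumed structure and not for a wrong structure.

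There is also an open choice. Whether the model converges is known only once it is fitted, with treatment, to the final data. SAP 7.5.1 leaves the replacement to be chosen at that point.

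**Working it through.** **1. Inputs.** Test: "This calculation is based on a two-sided test with alpha set at 0.05" (Protocol 8.1.2). Effects: "The analysis is estimated to provide 90% power to detect 2.75, 5.5 and 5.5 percentage points advantage over placebo" for 300, 600 and 900 mg/day. Variability: "a common standard deviation of 14 percentage points". Allocation: "matching placebo tablets in a ratio of 1:1:1:1". Contrast: "A MMRM with the contrast (-5, -1, 3, 3) will be used for the analysis" (SAP 7.5.1). About 400 completers. The SDs at Weeks 2, 4 and 8 are **not given**, so they are assumed and varied below.

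**2. The plan's own figure.** Contrast value: −5×0 − 1×2.75 + 3×5.5 + 3×5.5 = 30.25. SE = 14 × √(44/100) = 9.287. z = 30.25/9.287 = 3.257. Power = Φ(3.257 − 1.960) = 90.3%, which reproduces the stated 90%. The required size is 99.03 per arm, rounded up to 100, and 400/0.9 = 444.4 against 445 stated. The sample size is sound.

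**3. Effect of compound symmetry.** Take complete data and separate treatment means at each visit, and ignore the site and stratum terms. Compound symmetry then leaves the Week 12 estimate unchanged but replaces its variance by the average over the four visits. So:

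- R = (mean of the four visit variances) / (Week 12 variance)
- SE ratio = √R
- true two-sided size = 2 × [1 − Φ(1.96 × √R)]

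Only the SDs relative to Week 12 matter.

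| Assumed SDs, Weeks 2/4/8/12 | R | SE ratio | Size |
|---|---|---|---|
| 14/14/14/14 | 1.000 | 1.00 | 5.0% |
| 12/12.5/13/14 | 0.849 | 0.92 | 7.1% |
| 11/12/13/14 | 0.804 | 0.90 | 7.9% |
| 10/11/13/14 | 0.747 | 0.86 | 9.0% |
| 9/11/12.5/14 | 0.707 | 0.84 | 9.9% |
| 8/10/12/14 | 0.643 | 0.80 | 11.6% |
| 6/8/11/14 | 0.532 | 0.73 | 15.3% |

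Example, last row: (36 + 64 + 121 + 196)/4 = 104.25; 104.25/196 = 0.532; √0.532 = 0.73.

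**4. The SAP's random-slope form.** Let f be the residual share of the Week 12 variance. Then variance(t)/variance(12) = f + (1 − f)(t/12)². With f = 0, R = (1/36 + 1/9 + 4/9 + 1)/4 = 0.396 and the size is 21.8%. In general R = f + 0.396(1 − f). For f = 0.8, 0.6 and 0.4 the size is 6.6%, 8.8% and 11.8%.

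**5. Check with dropout.** REML simulation under the null: 111 per arm, 10% monotone dropout, no site or baseline covariates, 1,500 runs per compound symmetry scenario. SEs are for the contrast divided by 6, as in the SAP 13 code.

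| Scenario | Structure fitted | Mean model SE | Empirical SD | Rejection rate |
|---|---|---|---|---|
| Constant SD | compound symmetry | 1.51 | 1.48 | 4.4% |
| f = 0.6 | compound symmetry | 1.34 | 1.59 | 9.1% |
| f = 0.4 | compound symmetry | 1.22 | 1.54 | 11.1% |
| f = 0.25 | compound symmetry | 1.12 | 1.53 | 14.9% |
| f = 0.4 | heterogeneous compound symmetry (600 runs) | 1.51 | 1.56 | 5.5% |
| f = 0.4 | unstructured (300 runs) | 1.54 | 1.48 | 4.3% |

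The last two rows carry a Monte Carlo error of about 1 point. Allowing a separate variance at each visit restores the size.

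**6. How likely is the fallback?** Four visits need 4×5/2 = 10 covariance parameters. The site counts in SAP Appendix C sum to 20+53+49+52+61+71+51+36+65 = 458 FAS patients (36 is my sum for pooled site 8). Failure is unlikely. Overall size = 5% + p × (conditional size − 5%), where p is the chance that the fit fails and compound symmetry follows. With an illustrative p of 1% and a conditional size of 15.3%, that is 5% + 0.01 × 10.3% = 5.1%.

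If home SVC is modelled over all weekly windows in SAP Appendix B, there are 12 visits and 12×13/2 = 78 parameters, and SAP 7.9.3 acknowledges that use of the device varies between patients. The SAP 13 code note lists only Weeks 2, 4, 8 and 12, which would again mean 10.

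**The case against.** A reader might infer that the trial's primary test runs at a 9% to 15% false-positive rate. The documents do not support that. Three things must coincide: the unstructured fit fails, compound symmetry is chosen, and the variance grows about as assumed. The first is unlikely. The second is not required, because the SAP offers compound symmetry only as an example and as something that may be used, so better structures are already allowed. The third rests on SDs that the documents do not contain. All of this stands.

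A reader might also infer that every subgroup fit is exposed. SAP 7.3 restricts subgroups to those large enough to converge, which removes the smallest categories. Subgroups and home SVC also lie outside the closed test in SAP 7.4. The four-visit formula does not carry over to SAP 7.9.3.2, which uses continuous time and a location term, so nothing is quantified there.

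Finally, SAP 1 requires final-analysis decisions before database lock, and SAP 13 requires the final code to be settled by then. This narrows the room for choice but does not close it. Non-convergence shows only when the treatment model is fitted to final data, and neither section requires a ranked fallback to be written down first.

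**Conclusion.** The point holds as a minor one. The fallback is unordered, and its only named example is anti-conservative at Week 12 whenever the variance of change rises across visits. If compound symmetry were used in the four-visit model, the size of a nominal 5% test would lie between about 5% and about 22%. The 9% to 15% band corresponds to standard errors about 14% to 27% too small and depends on assumed SDs before Week 12. The random-slope models make growth plausible but do not fix its amount.

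For the primary analysis, and for ALSFRS-R under the same model, the overall type I error would move little. The fallback matters more for exploratory home SVC if all weekly visits are modelled, for the combined home and clinic model, and for smaller subgroups that meet the convergence condition in SAP 7.3.

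**What to change.** In SAP 7.5.1, replace the sentence with a fixed order to be followed on non-convergence: unstructured; then heterogeneous Toeplitz; then heterogeneous AR(1) or heterogeneous compound symmetry, with the choice between these two named in advance. The first structure that converges is used. Keep Kenward-Roger with model-based standard errors; if sandwich standard errors are preferred, state the degrees-of-freedom method. Remove equal-variance compound symmetry as the named example in both 7.5.1 and 7.9.3.2.

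Of the fallback structures, only heterogeneous compound symmetry was simulated here. The others are proposed because they also allow a separate variance at each visit. The cost is a few lines of SAP text and matching code in SAP 13; design and data collection are unaffected.

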7.5.2. Sensitivity Analyses of the Primary Efficacy Results

Sensitivity analysis under the assumption of missing not at random (MNAR) will be conducted using control-based pattern imputation approach ([Ratitch 2011](#)) for the primary efficacy endpoint (change from baseline to Visit Week 12 in percent predicted SVC). A model for imputing missing observations of percent predicted SVC in both reldesemtiv and placebo groups will be constructed using the observed data in the placebo group. The sensitivity analysis will include all observed and the aforementioned imputed data in the analysis model for the primary efficacy endpoint.

7.6. Analysis of the Secondary Efficacy Endpoints

Slope of muscle strength mega score over time through Week 12 will be analyzed for the FAS. The response variable will be muscle strength mega score at each post baseline visit up to Week 12. The model will include the following covariates:

- Treatment (reldesemtiv 300 mg/day, 600 mg/day and 900 mg/day, and placebo)
- Pooled site (Center)
- Time (time from the first dose, a continuous variable)
- Riluzole and edaravone use status at baseline
- Treatment-by-riluzole use status interaction
- Treatment-by-edaravone use status interaction
- Treatment-by-time interaction

The time will be set as a random effect and the intercept will be set to zero.

The Change from baseline to Visit Week 12 in ALSFRS-R will be analyzed using the same model as for the primary efficacy endpoint, except for the response variable.

7.7. Analysis of the Exploratory Efficacy Endpoints

Analyses for the exploratory endpoints specified in [Section 2.2.4](#) will be performed for the FAS.

The endpoints of change from baseline will be analyzed using the same model as described for the primary efficacy endpoint, except for the response variable.

The endpoint of percent change from baseline or muscle strength mega score (calculated as percent change in muscle strength from baseline) will be analyzed using the same model as described for the primary efficacy endpoint, except that the terms “baseline” and “baseline-by-visit interaction” will be excluded from the model.

The endpoints of slope of the change from baseline will be analyzed using a MMRM. The response variable will be the change from baseline to each post baseline visit up to Week 12. The model will include the following covariates:

- Treatment (reldesemtiv 300 mg/day, 600 mg/day and 900 mg/day, and placebo)
- Baseline (baseline value of the response variable)
- Pooled site (Center)
- Time (time from the first dose, a continuous variable)
- Riluzole and edaravone use status at baseline
- Treatment-by-baseline
- Treatment-by-time interaction

The time will be set as a random effect and the intercept will be set to zero.

The endpoints of slope of percent change from baseline, including slope of percent change in parameters of handwriting and voice recording, will be analyzed using the same model as for the slope of muscle strength mega score over time described in [Section 7.6](#).

